6.5.3 Dose modifications

For participants who do not tolerate the protocol-specified dosing schedule: dose interruptions (for sabatolimab, azacitidine and venetoclax), and/or dose reductions (azacitidine and venetoclax only) are either recommended or mandated in order to allow participants to continue the study treatment. Dose reductions for sabatolimab are not allowed.

Guidelines for permanent treatment discontinuation is mandatory for specific events indicated as such in Table 6-5 and Table 6-6.

Dose interruption at the start of a new treatment cycle

In participants who have achieved CR or mCR and have Grade 4 neutropenia and/or Grade 4 thrombocytopenia dosing of both venetoclax and azacitidine should be interrupted until resolution to \leq Grade 2. Sabatolimab should not be administered during the dose interruption. After resolution, dosing of both azacitidine and venetoclax should be resumed on the same day with dose modification for venetoclax as specified in Table 6-6. The first day dosing is resumed will be considered as D1 of the new treatment cycle and sabatolimab will be administered on

Day 8 of the new cycle. In cases in which venetoclax and azacitidine have been permanently discontinued and the participant remains on sabatolimab, then, in participants who have achieved CR or mCR and have Grade 4 neutropenia and/or Grade 4 thrombocytopenia, dosing of sabatolimab should be interrupted until resolution to \leq Grade 2. The first day dosing with sabatolimab is resumed will be considered D8 of the new cycle.

Dose modifications for sabatolimab

Dose modifications for sabatolimab will be done according to ASCO guidelines about management of immune-related AEs (Brahmer et al 2018).

Additionally, the guidance indicated in Table 6-5 below, provides instructions for infusion reaction, immune-related adverse events not covered by ASCO guidelines and a general guideline for non-hematologic non-immune-related toxicities that are clinically significant per investigator judgement and possibly attributable to the investigational drug. This general guideline will not apply in case of non-hematologic non-immune-related toxicities that are attributable to azacitidine, venetoclax and MDS and its complications.

Deviations to dose interruptions and/or permanent discontinuations outlined in Table 6-5 are not allowed.

Administration of sabatolimab may be delayed due to toxicities. A scheduled dose may be delayed within a cycle by up to 14 days. If a dose cannot be administered within the planned window within the cycle, then the dose should be skipped. Next scheduled dosing may resume once the adverse event has resolved to \leq Grade 1 or baseline per the next planned treatment cycle. Dose reductions for sabatolimab are not allowed.

Overall, for adverse events of potential immune-related etiology (irAE) that do not recover to \leq Grade 1 or baseline at a dose of immunosuppression of \leq 10 mg/day prednisone or equivalent (or as indicated in Table 6-5) within 12 weeks after initiation of immunosuppressive therapy, sabatolimab must be permanently discontinued.

Worst Toxicity Grade (CTCAE v5.0)	Recommended Dose Modifications
Infusion Reaction	
Grade 1	Decrease infusion rate until recovery
Grade 2	Stop infusion
	Before restarting – pre-medicate according to local institutional guidelines.
	Restart infusion at 50% of previous rate under continuous observation. Ensure that there is a minimum observation period of 1 hour prior to restarting the infusion(s). If the AE recurs at the reinitiated slow rate of infusion, and despite oral pre-medication*, then discontinue sabatolimab
Grade 3	Stop infusion
	If the AE resolves to \leq Grade 1 within 72hrs:

Table 6-5Criteria for dose interruption and re-initiation or discontinuations of
sabatolimab for adverse drug reactions

Worst Toxicity Grade (CTCAE v5.0)	Recommended Dose Modifications
	• At next scheduled treatment visit, pre-medicate according to local institutional guidelines.
	• Restart infusion at 50% of previous rate under continuous observation. Ensure that there is a minimum observation period of 1 hour.
	 If the AE recurs despite slow rate of infusion and pre-medication*, then discontinue sabatolimab.
	If the AE does not resolve to \leq Grade 1 within 72hrs:
	· Discontinue sabatolimab
Grade 4	Discontinue sabatolimab

For adverse events thought to be immune-related AEs and not covered in the ASCO Guidelines for the management of immune-related adverse events in participants treated with immune checkpoint inhibitor therapy (Brahmer et al 2018)

Grade 1	Continue treatment with sabatolimab
Grade 2 or Grade $3 \le 7$ days	Delay treatment with sabatolimab until resolved to ≤ Grade 1 or baseline
Grade 3 lasting > 7 days but < 21 days	1st and 2nd occurrence
	Delay study treatment until resolved to ≤ Grade 1 or baseline
	3rd occurrence:
	Discontinue study treatment
Grade 3 lasting ≥ 21 days Or Grade 4	Discontinue study treatment
Dermatological toxicities	
Grade 1	Maintain sabatolimab. Use topical steroids, antihistamines, topical emollients.
Grade 2	Consider interrupting sabatolimab.
	Use topical or oral steroids, antihistamines.
	If sabatolimab is interrupted and resolution to ≤ Grade 1, restart sabatolimab.
Grade 3 or 4	Interrupt sabatolimab.
	Manage per institutional practice.
	After resolution to \leq Grade 1, consider restarting sabatolimab.
Bullous dermatitis	Grade 1, 2 and 3: Interrupt sabatolimab. Consult with dermatologist for appropriateness to restart sabatolimab.
	Grade 4: Permanently discontinue sabatolimab.
Stevens-Johnson syndrome (SJS), or Lyell	Permanently discontinue sabatolimab.
syndrome/toxic epidermal necrolysis (TEN)	
For non-hematological, non immune related to	xicities clinically significant** and at least

For non-hematological, non immune related toxicities clinically significant** and at least possible attributable to sabatolimab (NCI CTCAE v5.0)

(The guideline does not apply to for toxicities attributable to azacitidine or venetoclax or the underlying MDS including its complications)

Worst Toxicity Grade (CTCAE v5.0)	Recommended Dose Modifications
Grade 1 and Grade 2 tolerable	Continue treatment with sabatolimab
Grade 2 intolerable (includes all Grade 2 events defined as DLT in Table 6 4) and Grade 3	1st or 2nd occurrence: · Interrupt sabatolimab until toxicity recovers to ≤ Grade 1 or baseline
	 Once recovered to ≤ Grade 1 or baseline restart sabatolimab at the same dose level and schedule
	AE resolution to ≤ Grade 1 or baseline must occur within a maximum period of 56 days since interruption, otherwise sabatolimab must be permanently discontinued.
	3rd occurrence:
	· Permanently discontinue sabatolimab
Grade 4	Discontinue sabatolimab

All dose modifications should be based on the available information and worst preceding toxicity *Prophylaxis regimens will include both paracetamol/acetaminophen and an antihistamine. **Per investigator judgement

Dose modifications for azacitidine

If azacitidine treatment is deemed by the investigator to possibly have contributed to an observed adverse event, the dose or schedule of azacitidine treatment may be modified within a cycle and/or for subsequent cycles or temporary/permanent interruptions of azacitidine treatment may be decided by the investigator according to local practice and/or the country-specific label guiding azacitidine use.

Dose modifications for venetoclax

If venetoclax treatment is deemed by the investigator to possibly have contributed to an observed adverse event, the dose or duration of venetoclax treatment may be modified according to the following guidelines:

Event	Occurrence	Action
Grade 4 neutropenia with or without fever or infection; or Grade 4 thrombocytopenia	Occurrence prior to achieving remission	Transfuse blood products, administer prophylactic and treatment anti-infectives as clinically indicated.
	First occurrence after achieving remission and lasting at least 7 days	Delay subsequent treatment and monitor blood counts. Administer granulocyte-colony stimulating factor (G-CSF) if
		clinically indicated for neutropenia.

Table 6-6Dose modifications for venetoclax

Event	Occurrence	Action
		Once the toxicity has resolved to Grade 1 or 2, resume venetoclax therapy at the same dose.
	Subsequent occurrences in cycles after achieving	Delay subsequent treatment and monitor blood counts.
	remission and lasting at least / days	Administer G-CSF if clinically indicated for neutropenia.
		Once the toxicity has resolved to Grade 1 or 2, resume venetoclax therapy at the same dose and the duration reduced by 7 days for each subsequent cycle.
Blood chemistry changes	-	Withhold treatment.
suggestive of TLS		If the event is resolved within 48 hours of last dose, treatment with venetoclax can be resumed at the same dose.
Events of clinical TLS or blood	-	Withhold treatment.
chemistry changes requiring more than 48 hours to resolve		Treatment should be resumed at a reduced dose (per the investigator discretion). When resuming treatment after interruption due to TLS, the instructions for prevention of TLS should be followed.
Grade 3 or 4 non-hematologic	First occurrence	Withhold treatment.
toxicities		Once the toxicity has resolved to Grade 1 or baseline level, venetoclax therapy may be resumed at the same dose.
	Subsequent occurrences	Withhold treatment.
		Treatment should be resumed at a reduced dose (per the investigator discretion).

Permanent discontinuation of study treatment

If the study treatment (i.e. sabatolimab + azacitidine + venetoclax) is interrupted for toxicities and the start of the subsequent study treatment cycle is delayed for more than 28 consecutive days (measured from the intended start date of the new cycle (Day 29 of the previous cycle), the participant should be discontinued from study treatment.

At any time during the study, participants unable to tolerate one or two of the study treatment drugs may continue study treatment with only the tolerated drug(s) provided the participant benefits per investigator's judgement.

These dose changes must be recorded on the appropriate CRF.

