6.1 Study treatment

In this study, the term "investigational drug" refers to the Novartis study drug, sabatolimab. The term "study treatment" refers to the combination of study drugs: sabatolimab plus venetoclax plus azacitidine.

All dosages prescribed, dispensed to the participant and all dose changes during the study including the reason for any component of the study treatment must be recorded on the appropriate eCRF page.

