6.5.4.3 Follow up on potential drug-induced liver injury (DILI) cases

Guidelines for follow-up on potential DILI cases are described in Table 6-7 and Table 6-8.

ALT	TBL	Liver Symptoms	Action
ALT increase withou	t bilirubin increase:		
If normal at baseline: ALT > 3 x ULN If elevated at baseline: ALT > 2 x baseline or > 200 U/L (whichever occurs first)	Normal For participants with Gilbert's syndrome: No change in baseline TBL	None	 No change to study treatment Measure ALT, AST, ALP, GGT, TBL, INR, albumin, CK, and GLDH in 48-72 hours. Follow-up for symptoms
If normal at baseline: ALT > 5 x ULN for more than two weeks If elevated at baseline:	Normal For participants with Gilbert's syndrome: No change in baseline TBL	None	 Interrupt study drug Measure ALT, AST, ALP, GGT, TBL, INR, albumin,

Table 6-7Follow-up of abnormal liver chemistry results

ALT	TBL	Liver Symptoms	Action
ALT > 3 x baseline or > 300 U/L			CK, and GLDH in 48-72 hours.
(whichever occurs first) for more than two weeks			- Follow-up for symptoms.
If normal at baseline:	Normal	None	- Initiate close monitoring and workup for
$ALT > 8 \times ULN$			competing
ALT increase with bi	ilirubin increase:	1	etiologies.
If normal at baseline:	TBL $> 2 \times ULN$ (or	None	- Study drug can be
$ALT > 3 \times ULN$	INR > 1.5)		restarted only it
If elevated at baseline:	For participants with Gilbert's syndrome:		identified and liver enzymes return to
ALT > 2 x baseline or > 200 U/L (whichever occurs first)	bilirubin		baseline.
If normal at baseline:	Normal or elevated	Severe fatigue,	
ALT > 3 x ULN		nausea, vomiting,	
If elevated at baseline:		pain	
ALT > 2 x baseline or > 200 U/L (whichever occurs first)			

Table 6-8	Action required for isolated total bilirubin elevation
-----------	--

Abnormality	Action required
Any elevation > ULN	Fractionate bilirubin, evaluate for cholestatic liver injury (ALP) or alternative causes of bilirubin elevation. Treat alternative causes according to local institutional guidelines
Grade 2 (>1.5 - 3.0 ULN)	Maintain treatment. Repeat LFTs within 48- 72 hours, then monitor LFTs weekly until resolution to \leq Grade 1 or to baseline

Abnormality	Action required
Grade 3 (>3.0 – 10 ULN)	Interrupt treatment. Repeat LFTs within 48- 72 hours, then monitor LFTs weekly until resolution to \leq Grade 1 or to baseline
Grade 4 (> 10 x ULN)	Discontinue study treatment

Confidential

If abnormalities are confirmed, close observation and follow-up are required:

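### For an isolated Grade 4 bilirubin rise, Table 6-6 allows venetoclax to resume (and says it should after a later event) where Table 6-8 stops all study treatment; no rule says which governs

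*Protocol*

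**What the plan says.** Two tables in the protocol can apply to the same liver event.

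**Table 6-6 (Section 6.5.3, venetoclax).** It applies "If venetoclax treatment is deemed by the investigator to possibly have contributed to an observed adverse event". One row covers "Grade 3 or 4 non-hematologic" toxicities as a single category, with no exception for bilirubin or other liver events.
- First occurrence: venetoclax is withheld, then "Once the toxicity has resolved to Grade 1 or baseline level, venetoclax therapy may be resumed at the same dose".
- Subsequent occurrences: venetoclax is withheld, then "Treatment should be resumed at a reduced dose (per the investigator discretion").

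**Table 6-8 (Section 6.5.4.3, liver follow-up).** It is titled "Action required for isolated total bilirubin elevation" and separates the grades.
- Grade 3 (above 3.0 and up to 10 x ULN): "Interrupt treatment. Repeat LFTs within 48- 72 hours, then monitor LFTs weekly until resolution to" Grade 1 or baseline.
- Grade 4 (above 10 x ULN): "Discontinue study treatment". The row has no restart provision.

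Section 6.1 says that study treatment "refers to the combination of study drugs: sabatolimab plus venetoclax plus azacitidine". The permanent-discontinuation paragraph of Section 6.5.3 spells out the same three drugs.

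**The concern.** An isolated total bilirubin above 10 x ULN, with venetoclax a possible contributor, meets both rows. One table opens the way back to venetoclax and the other closes it for all three drugs. A site that reads only the venetoclax table could re-dose after severe hyperbilirubinemia and believe itself compliant. What is at stake is participant safety and consistent conduct across sites. The CR-rate analysis, sample size and run-in stopping rule are not touched.

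**Working it through.** No arithmetic applies, so the check is a side-by-side reading of the two rules for isolated total bilirubin when venetoclax is a possible contributor.

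| Event | Table 6-6 (venetoclax) | Table 6-8 (study treatment) | Compatible? |
|---|---|---|---|
| Grade 3 | Withhold; resume after recovery to Grade 1 or baseline | Interrupt; monitor to Grade 1 or baseline | Yes, same threshold |
| Grade 4, first occurrence | Withhold; *may* resume at same dose after recovery | Discontinue | Both can be obeyed by stopping, but Table 6-6 permits what Table 6-8 rules out |
| Grade 4, subsequent occurrence | Withhold; *should* resume at reduced dose | Discontinue | No |

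The last line can be reached by a simple path. A participant has a Grade 3 bilirubin rise, recovers, and resumes venetoclax as both tables allow. A Grade 4 rise follows. Table 6-6 now directs resumption at a lower dose, and Table 6-8 directs a stop.

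Of the two grades merged in the Table 6-6 row, one conflicts with Table 6-8. At that grade Table 6-8 permanently stops three of three drugs and Table 6-6 permanently stops none.

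The next step was to look for a sentence that ranks the tables.
- Section 6.5.3 makes permanent discontinuation mandatory where Tables 6-5 and 6-6 indicate it. It does not name Table 6-8, and no row of Table 6-6 as printed orders permanent discontinuation.
- Section 6.5.3 also lets participants continue on whichever drugs they tolerate. It does not exempt Table 6-8 events.
- Section 6.5.4.3 introduces Tables 6-7 and 6-8 as follow-up guidelines for potential DILI and does not refer back to Table 6-6.
- Section 4.6 says dose modifications must be applied and points to Section 6.5.3, where Table 6-6 sits, not to Section 6.5.4.3.
- Section 6.5.2 lets a participant whose DLT resolves to Grade 1 or baseline continue after consulting the medical monitor. It makes no exception for bilirubin.
- Section 9.1.1 requires stopping in any situation that might pose a safety risk. This rests on judgement and does not say which table applies.

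None of these settles the precedence.

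**The case against.** The best defence is that the specific rule beats the general one. Table 6-8 deals with exactly this event and its title speaks of required action. Table 6-6 is introduced as guidance under which venetoclax *may* be modified, and at first occurrence it only permits resumption. A site that follows Table 6-8 then breaches nothing, and a careful investigator would probably do so. That stands for the first occurrence. It does not dispose of the later-occurrence cell, which says *should*. The reference to investigator discretion there may soften the direction, but it sits next to the dose reduction and does not clearly extend to whether to resume at all.

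The glossary defines study treatment discontinuation as permanently stopping any of the drugs, which could loosen the all-three reading of Table 6-8. Sections 6.1 and 6.5.3 define study treatment explicitly as the combination, and that is the better reading.

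A reader might infer more than the documents support:
- **That Section 6.5.3 makes Table 6-8 optional because it is not named there.** The sentence only makes discontinuation mandatory where the two named tables call for it. It is silent on Table 6-8.
- **That the 28-day cycle-delay rule fixes a time window for re-dosing.** That rule is triggered when the three-drug treatment is interrupted and the next cycle starts late. If only venetoclax is withheld, the other drugs may continue and the clock need not run.
- **That Tables 6-5 and 6-7 are part of the same conflict.** The non-immune row of Table 6-5 also stops sabatolimab at Grade 4, so it agrees with Table 6-8. The restart condition in Table 6-7 concerns other liver patterns, and its cell is too damaged in the available text to support a claim.

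**Conclusion.** The inconsistency is real and narrow. It concerns isolated total bilirubin above 10 x ULN when the investigator considers venetoclax a possible contributor. The instructions oppose each other directly for a subsequent occurrence. For a first occurrence Table 6-6 gives a permission that Table 6-8 does not allow. At Grade 3 there is no conflict.

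It is a minor participant-safety correction. The conclusion rests on the Section 6.1 meaning of study treatment and on the absence of any ranking sentence in the sections listed above. The documents give no frequency for the event. Part 1 planned about 18 participants (6 + 12). The SAP introduction records that recruitment was permanently halted in September 2022 and that the expansion will not open. Only run-in participants still on treatment can be affected, and the documents do not say how many there are.

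**What to change.** Two wording changes to the protocol:
1. In the Grade 3 or 4 non-hematologic row of Table 6-6, for both first and subsequent occurrences, add: except isolated Grade 4 total bilirubin elevation (> 10 x ULN), for which study treatment is discontinued per Table 6-8.
2. Add Table 6-8 to the Section 6.5.3 sentence on mandatory permanent discontinuation.

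Keep Table 6-6 in force for other liver events. A blanket hepatic exception would leave an isolated Grade 3 or 4 rise in AST, ALP or GGT without a venetoclax rule, because Tables 6-7 and 6-8 are triggered by ALT and by isolated bilirubin.

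The cost is a short amendment, with a letter alerting sites. Section 14.1 requires protocol changes to be made by written amendment, but allows those needed for participant safety to be implemented at once with notification afterwards. No new data are needed. If no participant remains on study treatment, the change has no practical effect in this trial.

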6.5.4 Follow-up for toxicities

Participants whose treatment is interrupted or permanently discontinued due to an AE or clinically significant laboratory value, must be followed-up at least once a week (or more frequently if required by institutional practices, or if clinically indicated) for 4 weeks, and subsequently at approximately 4-week intervals, until resolution or stabilization of the event, whichever comes first. Appropriate clinical experts should be consulted as deemed necessary.

All participants must be followed up for AEs (including irAEs and SAEs) for 30 days following the last dose of venetoclax or azacitidine (whichever was later) and 150 days following the last dose of sabatolimab, whichever is later.

6.5.4.1 Follow-up for immune-related AEs

The emergence of Immune-Related AE (irAE) may be anticipated based on general experience in clinical studies with similar class of compounds that block the negative immune regulators.

An irAE is any clinically significant AE affecting any organ that is associated with study drug exposure, is consistent with an immune-mediated mechanism, and where alternative explanations have been investigated and ruled out or are considered to be unlikely. Serologic, histologic and immunological assessments should be performed as deemed appropriate by the Investigator, to verify the immune related nature of the AE. An empiric trial of corticosteroids may also contribute to understanding the etiology of a potential irAE. All participants with signs or symptoms of irAEs should be monitored and managed following the ASCO Guidelines for the management of immune-related adverse events in participants treated with immune checkpoint inhibitor therapy (Brahmer et al 2018). See guidance in Table 6-5 for immune-related AEs not covered by ASCO guidelines.

In case of a suspected irAE, the relevant immunological assessments (e.g. rheumatoid factor, anti-DNA Ab, etc.) should be performed. In case of a toxicity suspected to be a cytokine release syndrome, the cytokine assessments outlined in Table 8-1 must be performed.

Participants should be monitored carefully for any skin toxicity or mucositis and study treatment should be discontinued for any suspected case of SJS/TEN.

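### For SJS/TEN the protocol does not give sites one stopping rule: one section stops all three drugs, the sabatolimab table stops sabatolimab only, and the DLT text allows treatment to continue once the event resolves

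*Protocol*

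**What the plan says.** - **Protocol 6.1** says the term study treatment "refers to the combination of study drugs: sabatolimab plus venetoclax plus azacitidine". SAP 2.1.1 uses the same three-drug meaning, and the permanent-discontinuation paragraph of Protocol 6.5.3 spells the three drugs out again.
- **Protocol 6.5.4.1** (follow-up of immune-related AEs): "study treatment should be discontinued for any suspected case of SJS/TEN".
- **Protocol 6.5.3, Table 6-5**, SJS/TEN row: "Permanently discontinue sabatolimab". No other drug is named. The text before the table adds: "Deviations to dose interruptions and/or permanent discontinuations outlined in Table 6-5 are not allowed".
- **Protocol 6.5.2 and Table 6-4** list severe skin reactions, with TEN and SJS as examples, as a DLT. After a DLT, study treatment must be interrupted and may be stopped for good depending on severity. If the event resolves to Grade 1 or baseline, the participant may go on with study treatment after consulting the sponsor's medical monitor.
- **Protocol 6.5.3, Table 6-6** (venetoclax), first Grade 3 or 4 non-hematologic toxicity: "Once the toxicity has resolved to Grade 1 or baseline level, venetoclax therapy may be resumed at the same dose".
- **Protocol 6.5.3, azacitidine text**, leaves changes to the investigator, local practice and the label.
- **Protocol 6.5.3, permanent discontinuation**, lets a participant who cannot tolerate one or two of the drugs continue on the rest if the investigator judges there is benefit.
- **Protocol glossary** counts permanently stopping any one of the drugs as study treatment discontinuation.

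**The concern.** SJS and TEN are among the few events the protocol names individually, and the instruction for them should be unambiguous. As written, the set of drugs to stop depends on the page the site opens. A site working from 6.5.4.1 stops three drugs on suspicion. A site working from Table 6-5 finds a mandatory stop for sabatolimab and nothing on the other two. A site working from the DLT section finds a route back to all three.

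The first consequence is for participant safety. The second is for the data:

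- The SAP's on-treatment period (2.6.2) ends 30 days after the last administration of study treatment, and SAP Section 4 takes that as the last non-zero dose of any component. Continuing venetoclax or azacitidine therefore lengthens the window in which AEs are counted.
- The end-of-treatment visit (Protocol Section 8) and entry into efficacy follow-up (8.3.1) are also triggered by stopping study treatment.

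**Working it through.** No figure in the plan depends on this point, so there is nothing to recompute. The check sets the passages side by side for one event, SJS/TEN, with study treatment read as Section 6.1 defines it.

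| Passage | Names SJS/TEN? | Trigger | Sabatolimab | Venetoclax and azacitidine |
|---|---|---|---|---|
| 6.5.4.1 | Yes | Any suspected case | Stop | Stop |
| Table 6-5, SJS/TEN row | Yes | The event | Stop permanently | Not mentioned |
| 6.5.2 with Table 6-4 | Yes, as a DLT | DLT in the run-in observation period | Interrupt; may continue once resolved | Same |
| Table 6-6 | No | First Grade 3 or 4 non-hematologic toxicity, venetoclax possibly contributory | Not covered | Venetoclax withheld, may resume |
| 6.5.3, permanent discontinuation | No | Intolerance of one or two drugs | Tolerated drugs may continue | Same |

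1. **6.5.4.1 against Table 6-5.** Same event, different drugs named. This is the core of the point.
2. **6.5.2 against both.** Study treatment includes sabatolimab, so the permission to continue after a resolved DLT also fails to match the permanent stop in Table 6-5. Section 6.5.2 makes no exception for SJS/TEN.
3. **The general rules.** Neither Table 6-6 nor the tolerated-drug permission excludes SJS/TEN. Section 6.5.3 opens by pointing sites to Tables 6-5 and 6-6 for mandatory permanent discontinuations, but Table 6-6 contains no permanent-discontinuation action and the sentence does not mention 6.5.4.1.
4. **Is it only loose wording?** Table 6-5 is titled for sabatolimab, yet its immune-related rows use both terms. Grade 2, or Grade 3 up to 7 days, delays sabatolimab. Grade 3 lasting more than 7 but under 21 days delays study treatment, and a third occurrence discontinues it. The last row reads "Grade 3 lasting ≥ 21 days Or Grade 4 Discontinue study treatment". Because the table uses both terms, a reader cannot assume they are interchangeable in the SJS/TEN row. The table also does not say whether the tolerated-drug permission still applies once a row has said to stop study treatment.
5. **Precedence.** None of these passages states which one governs when they differ.

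**The case against.** The strongest reply is that 6.5.4.1 and Table 6-5 can both be obeyed. The table is about sabatolimab, so its silence on the other two drugs is not an instruction to continue them, and stopping all three drugs also satisfies the sabatolimab row. That is correct. It rules out saying that sites cannot comply. It does not tell a site that starts from the tables that a wider instruction exists elsewhere, and it does not deal with the DLT text. Section 9.1.1 requires stopping for a safety risk, but leaves that to case-by-case judgement.

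The glossary might be offered as a cure, since it counts stopping any drug as study treatment discontinuation. It defines a status for reporting, not which drugs to stop, and it does not fit Section 6.1. It adds an ambiguity.

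Several stronger readings are tempting but not supported:

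- **That Table 6-6 expressly lets venetoclax resume after SJS/TEN.** It is a general and permissive rule that names neither SJS/TEN nor immune-related events, and it applies only if the investigator thinks venetoclax possibly contributed. What stands is the missing exception.
- **That the rules for severe immune-related events contradict each other in the same way.** The move from sabatolimab to study treatment begins at Grade 3 beyond 7 days and holds through Grade 4, which reads as a severity gradient. The 12-week non-recovery sentence is a separate trigger for stopping sabatolimab. These rows cover only events outside the ASCO guideline, which is not in the documents. What stands is the unexplained mix of terms.
- **That DLT evaluability is affected.** SJS/TEN is itself a listed DLT, and a participant with a DLT in the observation period is evaluable whichever drugs are then stopped (6.5.1.3, 12.1; SAP 2.2.3).

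**Conclusion.** The point holds for SJS/TEN: sites are not given one stopping rule. Section 6.5.4.1, the SJS/TEN row of Table 6-5, and Section 6.5.2 with Table 6-4 give three different outcomes, two general rules carry no exception, and precedence is not stated.

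Its weight is in participant safety and uniform conduct. The CR estimand counts remissions regardless of discontinuation of any component (Protocol 12.4.1.2; SAP 2.5.1.2), so the primary efficacy analysis is untouched, as are the sample size and the dose decision.

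A reader might infer a numerical effect, for example that one event in a cohort of about 12 shifts the rate of study treatment discontinuation by 1/12 = 8.3 percentage points. The documents do not support that. The event is hypothetical, and under the glossary definition the shift is 0, because stopping sabatolimab alone already counts. The SAP also reports AEs leading to study treatment or sabatolimab discontinuation (2.6.2.1) and permanent discontinuations by component (2.4.1.4), so part of the difference would be visible.

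The conclusion rests on reading study treatment as Section 6.1 defines it. The SAP introduction records that recruitment was halted in September 2022 and that the expansion will not open, which limits the reach to participants still treated and to the coding of discontinuations.

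**What to change.** The sponsor's clinical team should reconcile Section 6.5.2 with Table 6-4, the SJS/TEN row and immune-related rows of Table 6-5, Table 6-6, the permanent-discontinuation text of 6.5.3, and 6.5.4.1. Specifically:

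- For each action, name the drug or drugs it applies to.
- State which passage takes precedence for SJS/TEN, and whether suspicion alone is the trigger.
- Say whether the tolerated-drug permission applies where a row stops study treatment.
- Use 'study treatment' only in its Section 6.1 meaning, and align the glossary entry for study treatment discontinuation.

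Which rule should apply is a clinical decision for the sponsor and is not proposed here. The cost is clarifying wording in an amendment or a letter to sites, with no new procedures or data collection. For the abbreviated report, one line in the SAP stating which definition is used to count study treatment discontinuation would be enough.
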